# Ocrelizumab—F. Hoffmann-La Roche Ltd

Protocol WA39085, Version 10

### **PROTOCOL HISTORY**

Protocol		
Version	Date Final	
10	See electronic date stamp on the final page of this document.	
9	18 July 2023	
8	15 March 2023	
7	3 June 2021	
6	18 January 2021	
5	2 February 2020	
4	28 August 2019	
3	26 June 2019	
2	16 April 2019	
1	20 April 2017	

## PROTOCOL AMENDMENT, VERSION 10 RATIONALE:

Protocol WA39085 has been amended to extend the duration of the safety follow-up period to 104 weeks throughout the protocol to address postmarketing requirements from the United States Food and Drug Administration (FDA). Also as requested by the FDA, the definition of the exposure period has been added and analysis considerations have been specified (Section 6.6).

#### **PROTOCOL SYNOPSIS**

PROTOCOL TITLE:	AN OPEN-LABEL, PARALLEL-GROUP STUDY TO EVALUATE
	SAFETY, TOLERABILITY, PHARMACOKINETICS, AND
	PHARMACODYNAMIC EFFECTS OF OCRELIZUMAB IN
	CHILDREN AND ADOLESCENTS WITH RELAPSING-REMITTING
	MULTIPLE SCLEROSIS
REGULATORY	IND Number: 100,593
AGENCY	EudraCT Number: 2016-002667-34
IDENTIFIERS	EU CT Number: 2023-505269-10-00
	NCT Number: NCT04075266

#### STUDY RATIONALE

The purpose of this study is to evaluate the safety, tolerability, pharmacokinetics, and pharmacodynamic effects of ocrelizumab in children and adolescents ages  $\geq$  10 to < 18 years with relapsing-remitting multiple sclerosis (RRMS). The data from this study will serve to determine the dosing regimen of ocrelizumab to be further investigated in the subsequent Phase III study in children and adolescents.

#### **OBJECTIVES AND ENDPOINTS**

Primary Objectives			
Primary Pharmacokinetic Objectives	Corresponding Endpoint		
To characterize the ocrelizumab PK profile in children and adolescents	
 
Serum concentration of ocrelizumab at specified timepoints
 
		
Primary Pharmacodynamic Objective:	Corresponding Endpoint		

 
To evaluate relationship between drug exposure and PD (CD19+ B-cell count) in children and adolescents
 
	Levels of CD19 + B-cell count in blood		
Secondary Objectives			
Secondary Safety Objectives	Corresponding Endpoints		

 
To evaluate safety of ocrelizumab in children and adolescents
 
	Occurrence and severity of adverse events, with severity determined according to NCI CTCAE v5.0		
	Change from baseline in vital signs		
	Change from baseline in clinical laboratory test results		
	
 
Level of circulating B cells, T cells, natural killer cells, and other leukocytes
 
		
	
 
Developmental milestones (e.g., growth, bone age, age at menarche, Tanner staging)
 
		
	
 
Non-MS CNS pathology as measured by brain MRI scans
 
		
	Levels of blood immunoglobulins		
	Antibody titers against standard vaccines		

Secondary Immunogenicity Objective	Corresponding Endpoint

 
To assess ADA development to ocrelizumab
 
	Presence of ADAs during the study relative to the presence of ADAs at baseline

ADA = anti-drug antibody; MRI = magnetic resonance imaging; MS = multiple sclerosis; NCI CTCAE v5.0 = National Cancer Institute Common Terminology Criteria for Adverse Events, Version 5.0; PD = pharmacodynamic; PK = pharmacokinetic.

#### **OVERALL STUDY DESIGN AND STUDY POPULATION**

This Phase II, open-label, parallel-group, study will evaluate the safety, tolerability, pharmacokinetics, and pharmacodynamic effects of ocrelizumab in children and adolescents with RRMS.

Phase:	Phase II	Population Type:	Pediatric patients
Control Method:	None	Population Diagnosis or Condition:	Relapsing-remitting multiple sclerosis
Interventional Model:	Parallel group	Population Age:	≥ 10 years and, < 18 years
Test Compound:	Ocrelizumab	Site Distribution:	Multi-site and multi-region
Active Comparator:	Not applicable	Study Intervention Assignment Method:	Open-label
Number of Cohorts:	2	Number of Participants to Be Enrolled:	Up to a maximum of 36

#### STUDY TREATMENT

Patients with a body weight from  $\ge 25$  kg to <40 kg (Cohort 1) will receive 300 mg ocrelizumab and patients with a body weight  $\ge 40$  kg (Cohort 2) will receive 600 mg ocrelizumab as follows:

- The initial dose of ocrelizumab will be administered as two IV infusions given 14 days apart (i.e., Cohort 1: 2×150 mg for a total dose of 300 mg and Cohort 2: 2×300 mg for a total dose of 600 mg) to minimize infusion-related reactions upon the first administration of ocrelizumab.
- Subsequent doses will be administered as single infusions (i.e., Cohort 1: 1 × 300 mg and Cohort 2: 1 × 600 mg).

#### **DURATION OF PARTICIPATION**

The duration of participation for an individual, from screening to the end of the SFU period (excluding the B-cell monitoring period because it is not known how long it takes for B cells to replete in the pediatric MS population after treatment with ocrelizumab) is expected to be approximately 402 weeks (~8 years).

#### COMMITTEES

Independent Committees:	Internal Monitoring Committee
Other Committees:	Not applicable

#### Abbreviation Definition ADA anti-drug antibody ADEM acute disseminated encephalomyelitis ARR annualized relapse rate AUC Area under the concentration-time curve **AUC**ss AUC at steady state AUC0-t AUC from time 0 to last quantifiable timepoint β-hCG beta-human chorionic growth hormone CD cluster of differentiation CDI confirmed disability improvement CDP confirmed disability progression CNS central nervous system Cmax maximum plasma concentration $C_{\text{trough}}$ minimum plasma concentration **AUC**ss AUC at steady state CSF cerebrospinal fluid DMT disease-modifying therapy EC **Ethics Committee** eCRF electronic case report form EDC electronic data capture EDSS Expanded Disability Status Scale ETDRS Early Treatment Diabetic Retinopathy Study FSS **Functional System Score** GA glatiramer acetate Gd gadolinium HBcAb hepatitis B core antibody HBsAg hepatitis B surface antigen HBV hepatitis B virus HepCAb hepatitis C antibody HIPAA Health Insurance Portability and Accountability Act IFN interferon immunoglobulin lg IMC Internal Monitoring Committee IMP **Investigational Medicinal Product** ICH International Council for Harmonisation IND Investigational New Drug (application) IPMSSG International Pediatric Multiple Sclerosis Study Group

#### LIST OF ABBREVIATIONS AND DEFINITIONS OF TERMS

Abbreviation	Definition
IRB	Institutional Review Board
IRR	infusion-related reaction
IWRS	interactive Web-based response system
JCV	JC–virus
KLH	keyhole limpet cyanin
LCVA	low-contrast visual acuity
LLN	lower limit of normal
LPLV	last patient, last visit
mAb	monoclonal antibody
MN	mobile nursing
MOG	myelin oligodendrocyte glycoprotein
MRI	magnetic resonance imaging
MS	multiple sclerosis
NAbs	neutralizing antibodies
NCI CTCAE	National Cancer Institute Common Terminology Criteria for Adverse Events
OLE	open-label extension
OOE	optional ocrelizumab extension
PCR	polymerase chain reaction
PD	pharmacodynamic
PK	pharmacokinetic
PML	progressive multifocal leukoencephalopathy
PPMS	primary progressive multiple sclerosis
PRMS	progressive-relapsing multiple sclerosis
RBR	Research Biosample Repository
RMS	remitting multiple sclerosis
RRMS	relapsing-remitting multiple sclerosis
SDMT	Symbol Digit Modalities Test
SFU	safety follow-up period
SPMS	secondary progressive multiple sclerosis
ТВ	tuberculosis
TSH	thyroid-stimulating hormone
ULN	upper limit of normal
WES	whole-exome sequencing
WGS	whole-genome sequencing

## 1. BACKGROUND

### 1.1 BACKGROUND ON MULTIPLE SCLEROSIS

Multiple sclerosis (MS) is a chronic, inflammatory, and demyelinating disease of the CNS that affects approximately 2.3 million people worldwide (MSIF 2013). Although MS is a global disease, its prevalence increases with distance from the equator. The prevalence of MS is highest in North America and Europe (140 and 108 per 100,000 people, respectively) and lowest in sub-Saharan Africa and East Asia at 2.1 and 2.2 per 100,000 people, respectively (MSIF 2013). MS typically begins between the ages of 20 to 40 years (Tullman 2013). Overall, women are affected approximately twice as often as men, except in individuals with the primary-progressive form of the disease, where there is no gender prevalence difference (MSIF 2013; Tullman 2013).

MS is a serious, disabling disease and the leading cause of non-traumatic disability in young adults (Tullman 2013). The disease course culminates in deterioration of physical and cognitive functions of patients, which significantly impacts quality of life and independence. Patients suffer from a range of MS-associated symptoms including motor weakness, spasticity, gait and coordination imbalance, sensory dysfunction, vision loss, sexual dysfunction, fatigue, depression, chronic pain, sleep disorders, and cognitive impairment (Damal et al. 2013). Diagnosis of MS is based on the application of structured diagnostic criteria that rely on clinical observation, neurologic examination, brain and spinal cord magnetic resonance imaging (MRI) scans, and at times evoked potential tests, and cerebrospinal fluid (CSF) examination (Polman et al. 2011; Thompson et al. 2018).

Prognosis is highly variable, and if left untreated, half of patients with MS would require assistance to walk within 15 years of disease onset (Expanded Disability Status Scale [EDSS] score > 6.0). MS also imposes a substantial economic burden on patients, their families, and society as a whole (Trisolini et al. 2010; Adelman et al. 2013). The cost of MS, including the impact on employment (such as reduced working hours or early retirement) and major investment in equipment (such as wheelchairs or housing modifications), has been shown to increase more than 3- or 4-fold for patients with severe disease (EDSS < 7.0) compared with patients with less severe disease (EDSS < 4.0) (Kobelt et al. 2006a; 2006b). The potential risk of irreversible disease progression is therefore an important factor in the therapeutic decision–making of patients and their physicians (Gold et al. 2010).

For the past two decades, MS has been clinically subcategorized into four phenotypic disease patterns distinguished by the occurrence and timing of episodes of transient neurologic compromise (relapses) relative to disease onset and disability progression (Lublin and Reingold 1996): relapsing–remitting MS (RRMS), secondary progressive MS (SPMS), primary progressive MS (PPMS), and progressive-relapsing MS (PRMS). A recently proposed revision to this classification recommends that the term PRMS be dropped, as it is considered vague and overlapping with other disease course subtypes,

# Ocrelizumab—F. Hoffmann-La Roche Ltd

17/Protocol WA39085, Version 10

and that PRMS and PPMS should therefore no longer be considered distinct entities but rather characterized both as PPMS, with or without activity (Lublin 2014). More recently, it has been proposed that PPMS is not a separate entity but rather a part of the spectrum of progressive disease (Ontaneda and Fox 2015), and as such RRMS and PPMS can be considered closely related diseases.

### 1.1.1 Features of Pediatric Multiple Sclerosis

Pediatric onset MS is rare, with between 3% and 5% of patients with MS having their first symptom before reaching the age of 18 years (Chitnis et al. 2012). During childhood and adolescence, the CNS goes through several developmental steps, including ongoing myelination. Therefore, MS–related inflammatory demyelination may result in atypical or incomplete formation of white matter pathways. Probably because of the brain maturation process and myelin immaturity, children have a distinctive clinical course, neuroimaging features, and laboratory results compared with adult-onset MS. Pediatric–onset MS appears to have more inflammatory activity.

Optic neuritis is a common presenting symptom in adolescents. Encephalopathy, seizures, and polyfocal (polyregional) onset occur as the initial manifestation more frequently in children than in adults. Children tend to experience their second (MS–defining) clinical exacerbation more rapidly than adults; approximately 40% of children will be diagnosed within 1 year of initial symptoms, 60% by 2 years, and 66% by 3 years. In comparison, approximately 45% of adults will be diagnosed within 2 years after onset of symptoms, and approximately 50% will be diagnosed within 3 years. Residual physical disability after the initial demyelinating event is present in less than 10% of children, while residual deficits from initial relapse may occur in up to 25% of adults (Banwell 2013).

As compared with adult MS where approximately 85% of patients have RRMS, more than 95% of pediatric patients have a relapsing-remitting course (Boiko et al. 2002; Banwell et al. 2007). Several studies have demonstrated that individuals with pediatric onset MS have slower progression of physical disability than those with adult onset, particularly during the early stages of the disease (Boiko et al. 2002; Simone et al. 2002; Trojano et al. 2004; Renoux et al. 2007; Harding et al. 2012). This discrepancy may suggest greater plasticity, less neurodegeneration, and potentially more capability for repair and remyelination in the younger CNS (Gorman et al. 2009). Although the time to secondary progressive disease and neurologic disability may take longer to achieve relative to adult-onset MS, it is important to keep in mind that the age at which pediatric onset patients experience progressive disease and disability is ultimately younger (Boiko et al. 2002). Finally, PPMS, is exceedingly rare in children (Ghezzi et al. 1997; Boiko et al. 2002; Simone et al. 2002; Waubant and Chabas 2009).

Fatigue is one of the most common problems that affect children and adolescents with MS, and it has been reported in over 60% of patients (MacAllister et al. 2009). Depression is also often associated with fatigue (Goretti et al. 2012).

Ocrelizumab—F. Hoffmann-La Roche Ltd 18/Protocol WA39085, Version 10 Cognitive impairment is increasingly recognized in children and adolescents with MS. Up to 35% of pediatric patients with MS have some identifiable cognitive dysfunction at the time of diagnosis, and about 50% of children continue to accrue cognitive deficits within the 5 years after disease onset (MacAllister et al. 2005; Ghezzi et al. 2010; Julian et al. 2013; Charvet et al. 2014). Cognitive deficits may include problems with general mentation, attention and information processing, language, visual motor integration skills, and verbal and visual memory (Kalb et al. 1999; Banwell and Anderson 2005; Suppiej and Cainelli 2014).

Fatigue and cognitive impairment are associated with limitations in social, academic, and recreational activities. Some patients have to repeat a year of school because of missed school days or academic difficulties (Ghezzi et al. 2010). The ability to engage in hobbies and sport activities can also be negatively affected.

The definitions proposed by the International Pediatric MS Study Group (IPMSSG) for the diagnosis of pediatric MS and other pediatric demyelinating disorders were revised in 2012 to incorporate advances in research and to include components of the 2010 revision of the McDonald criteria, given that pediatric-onset MS is formally included in the revised McDonald criteria (Polman et al. 2011; Krupp et al. 2013; Pena and Lotze 2013). The 2012 IPMSSG criteria (but not the McDonald 2010 criteria) required an age of 12 years or older for applying dissemination in time and dissemination in space criteria to diagnose MS at the time of the initial clinically isolated syndrome. Recently, it has been proposed to incorporate in IPMSSG criteria the 2010 McDonald criteria for MS for children of all ages, when MRI-defined dissemination in time and dissemination in space requirements for MS are present at the first attack, provided that the sentinel event is consistent with acute demyelination and that the attack does not conform with the criteria of acute disseminated encephalomyelitis (ADEM) (Tardieu et al. 2016).

### 1.1.2 Therapies and Prevention Strategy in Pediatrics

Current treatment strategies in pediatric MS are similar to those employed in adults. They focus on the treatment of acute relapses, disease modification, and treatment of MS symptoms.

Therapy of acute relapses is reserved for children in whom the symptoms of demyelination impair function or cause discomfort. Mild symptoms that do not impair function are not always treated. On the basis of experience in adults, glucocorticoids are standard first-line treatments (usually IV methylprednisolone), with IV immunoglobulin (Ig) as a second-line therapy for children who either fail to respond to glucocorticoids or have contraindications to their administration (Pena and Lotze 2013; Banwell 2013).

Despite the lack of formal clinical trials, injectables interferon (IFN) beta and glatiramer acetate (GA) are frequently used as first line treatment for pediatric patients with MS (Ghezzi et al. 2016). The three IFN beta agents (two IFN beta-1a and one IFN beta-1b)

Ocrelizumab—F. Hoffmann-La Roche Ltd 19/Protocol WA39085, Version 10 are approved in the European Union for the use in adolescent patients with relapsing MS aged 12 years and above on the basis of studies suggesting that the safety profile in adolescents is similar to that seen in adults. Recently in 2018, the U.S. Food and Drug Administration and European Commission have approved Gilenya® (fingolimod) to treat relapsing–remitting MS in children and adolescents 10 to 17 years old following the completion of the first clinical trial of fingolimod in pediatric patients with MS.

Studies have demonstrated that tolerability and efficacy of disease-modifying therapies (DMTs) in pediatric patients with MS have been reported to parallel those seen in adults (Chitnis 2013; Tenembaum et al. 2013; Narula et al. 2015). About 40% of pediatric patients with MS discontinue treatment because of intolerance, toxicity, persisting relapses, or non-adherence, supporting a need for developing new therapies in this population (Pena and Lotze 2013).

In cases of inadequate treatment response to the IFN or GA, alternative treatment options include changing between these therapies or switching to more potent immunomodulators. Oral medications with novel mechanisms of action, which have been approved for MS in adults (e.g., teriflunomide and dimethyl fumarate), are not routinely used in pediatric patients at this time given the limited data regarding the safety and efficacy of these treatments in children (Chitnis et al. 2012; Pena and Lotze 2013; Narula et al. 2015).

Given the potential severe long-term consequences of pediatric-onset MS, the current recommendation from IPMSSG is that children and adolescents with MS should have access to treatments currently approved for adults, and therapy should be started as early as possible in the disease course (Chitnis et al. 2012).

With the availability of more potent DMTs, the ultimate therapeutic goal would be to achieve a complete remission of clinical and MRI activity in the absence of tolerability or safety issues, through optimization of drug treatment early in order to prevent the consequent eventual accrual of disability and accumulation of cognitive deficits (Thomas and Banwell 2008; Narula et al. 2015).

# 1.2 BACKGROUND ON OCRELIZUMAB

Ocrelizumab is a recombinant humanized mAb that selectively depletes cluster of differentiation (CD)20–expressing B cells (Kappos et al. 2011; Klein et al. 2013). CD20 is a cell surface antigen found on pre–B cells and mature and memory B cells but not expressed on lymphoid stem cells and plasma cells (Stashenko et al. 1980; Loken et al. 1987, Tedder and Engel 1994). Although ocrelizumab selectively depletes CD20–expressing B cells, the capacity for B–cell reconstitution and preexisting humoral immunity are preserved (Martin and Chan 2006; DeLillo et al. 2008). In addition, innate immunity and total T–cell numbers are not affected.

The precise mechanisms through which ocrelizumab is thought to exert its therapeutic clinical effects in MS are not fully elucidated but involve immunomodulation through reduction in the number and function of B cells. These changes are thought to be responsible for the consequent improvement in the disease course of MS (Avivi et al. 2013).

## 1.2.1 Nonclinical Information

Repeat-dose toxicology studies of ocrelizumab at doses of up to 100 mg/kg, administered as 2 doses every 2 weeks (Days 1 and 15), 4 doses weekly (Days 1, 8, 15, and 22), or 8 doses every 3 weeks (Days 1, 22, 43, 64, 85, 106, 127, and 148), have been conducted. An embryo–fetal development study, a pre– and post–natal development study, male and female fertility studies, and a juvenile toxicity study in cynomolgus monkeys have also been completed.

In general toxicology studies, no adverse ocrelizumab–associated findings were identified, and pharmacological findings were consistent with the anticipated depletion of B cells in peripheral blood and lymphoid tissues. However, the following two studies did identify adverse findings that may be secondary to ocrelizumab-associated immunosuppression.

In a pre– and post–natal development study in cynomolgus monkeys, administration of ocrelizumab (15/20 and 75/100 mg/kg loading/study doses, which correspond to human equivalent doses of approximately 3000 mg [approximately 5×clinical dose] and 15000 mg [approximately 25×clinical dose], respectively) was associated with glomerulopathy (7 of 24 animals), lymphoid follicle formation in bone marrow (9 of 24 animals), and lymphoplasmacytic inflammation in the kidney (2 of 24 animals). Testicular weights of the neonates were significantly reduced in the 75/100 mg/kg group compared with controls. There were two cases of moribundity on study (2 of 24), one attributed to weakness due to premature birth accompanied by opportunistic infection and the other to an infective meningoencephalitis involving the cerebellum of the offspring from a maternal dam with an active infection (mastitis). The course of both neonatal infections could have potentially been affected by B–cell depletion. Newborn offspring of maternal animals exposed to ocrelizumab were noted to have depleted B–cell populations during the postnatal phase.

In an 8-week juvenile immunotoxicology study in cynomolgus monkeys, administration of ocrelizumab was associated with one mortality and one moribundity resulting in early euthanasia, both occurring in high-dose male cage-mates (100 mg/kg/week) and both occurring relatively early in the recovery period prior to recovery of peripheral blood B cells. Immunosuppression, secondary to the pharmacologic mechanism of action of ocrelizumab, B-cell depletion, is considered likely to have been an important contributing factor in both cases. No other deaths were observed in the study; all remaining animals survived to completion of the study. Ante-mortem immunophenotyping and postmortem microscopic findings confirmed ongoing

Ocrelizumab—F. Hoffmann-La Roche Ltd 21/Protocol WA39085, Version 10 B-cell depletion leading to immunosuppression in both animals; however, the degree of B-cell depletion in peripheral blood and lymph nodes were not remarkable relative to other monkeys in this dose cohort. There was also evidence of generalized stress and debilitation in both animals. In the animal euthanized moribund, clinical pathology parameters and anatomic pathology findings consistent with a systemic inflammatory process were suggestive of breakdown of intestinal mucosal barrier function and the potential for systemic extension of intestinal endotoxemia and/or enteric infection, which could have developed secondary to immunosuppression. Of note, during the dosing period, all animals on study were 9–13 months of age, which in cynomolgus monkeys is roughly equivalent to a 4-year-old human in terms of overall development. Although the immune system is reasonably developed and humoral immunity is functional at this age, this is still a presumed period of heightened susceptibility as immune memory takes time to develop as host exposure to multiple foreign challenges occurs slowly over time, particularly for young study animals housed in controlled laboratory conditions. Therefore, the unique susceptibilities in this animal population due to lack of cumulative adaptive immune memory are not representative of the risk to the proposed pediatric population, in which a robust exposure to common pathogens during the first decade of life have occurred.

In the juvenile immunotoxicology study, although ocrelizumab did suppress T-dependent antibody responses to keyhole limpet cyanin (KLH), there was no evidence of lasting effects on humoral immunity as there was no ocrelizumab-associated effect on a neo-antigen challenge (tetanus toxoid) when antigen was administered following a recovery period (drug clearance and full B-cell recovery). In this study, 20 mg/kg was considered to be the no observable adverse effect level, which provides the following safety factors over the estimated exposures in the proposed pediatric trial:

- Maximum plasma concentration (Cmax) at 20 mg/kg was 5-fold above projected Cmax in pediatric trial
- Area under the concentration-time curve (AUC) from time 0 to last quantifiable timepoint (AUC0-t) at 20 mg/kg was 13-fold above projected AUC at steady state (AUCss) in pediatric trial.

For details of the completed nonclinical ocrelizumab program, see the current Ocrelizumab Investigator's Brochure.

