#### 4.5.19.1 Local Laboratory Assessments

Samples for the following laboratory tests will be sent to the study site's local laboratory for analysis:

- Urinalysis: A urine dipstick for blood, protein, nitrite, and glucose (using the dipsticks provided) will be performed according to the schedule of activities (see Appendix 1). If abnormal and applicable, a microscopic examination will be performed on site (local laboratory).
- Pregnancy test: Urine pregnancy test (sensitivity of at least 25 mIU/mL β–hCG) for all females of childbearing potential (Tanner Stage 2 or above or onset of menarche during the study)

On infusion visits, the urine samples for the urinalysis and pregnancy test should be performed prior to the methylprednisolone infusion and the ocrelizumab dose withheld for a positive pregnancy test result.

A positive urine pregnancy test should be confirmed with a serum test through the central laboratory prior to any further dosing with ocrelizumab.

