## 4.5.19.2 Central Laboratory Assessments

In order to ensure patient safety in the study and to allow for assessments of the retreatment criteria, a central laboratory will provide study investigators and Medical Monitors with reflex messages triggered by critical laboratory results.

The reflex messages from a central laboratory, together with laboratory results, should be carefully reviewed at every visit before continuing with ocrelizumab treatment.

Investigators notified of a patient's critical laboratory test results will be instructed to suspend further treatment with study drug until the patient becomes eligible for re-treatment (see Section 4.3.6).

The reflex messages will be in effect during the entire study duration. Further details will be provided in the Laboratory Manual.

- Hematology: WBC count (absolute and differential), RBC count, RBC morphology, hemoglobin, hematocrit, quantitative platelet count, and ANC count
- Blood chemistry: AST, ALT, gamma glutamyl transferase, alkaline phosphatase, amylase, lipase, total protein, albumin, cholesterol, total bilirubin (direct and indirect will be performed if total bilirubin is greater than the ULN), uric acid, potassium, sodium, chloride, calcium, phosphorus, LDH, CPK, and triglycerides

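### The scheduled chemistry panel has no creatinine or urea, so filtration cannot be estimated from scheduled tests, although Section 1.2.1 reports kidney findings in monkeys

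*Combined protocol and SAP*

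**What the plan says.** Section 1.2.1 (Nonclinical Information) describes a pre- and post-natal development study in cynomolgus monkeys at two dose levels, equated to about 5 and 25 times the clinical dose. Ocrelizumab "was associated with glomerulopathy (7 of 24 animals" and with "lymphoplasmacytic inflammation in the kidney (2 of 24 animals". The section introduces this as one of two studies whose adverse findings may follow from the immunosuppression that the drug causes. Of the other repeat-dose work it says: "In general toxicology studies, no adverse ocrelizumab–associated findings were identified".

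Section 4.5.19.2 (Central Laboratory Assessments) gives the chemistry panel as a single list. It opens "Blood chemistry: AST, ALT, gamma glutamyl transferase, alkaline phosphatase, amylase, lipase, total protein, albumin, cholesterol, total bilirubin" and, after a reflex for direct and indirect bilirubin, closes "uric acid, potassium, sodium, chloride, calcium, phosphorus, LDH, CPK, and triglycerides".

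Section 4.5.19.1 gives urinalysis to the local laboratory: "A urine dipstick for blood, protein, nitrite, and glucose (using the dipsticks provided) will be performed according to the schedule of activities". Microscopy follows if the dipstick is abnormal and microscopy is applicable. The footnotes to Appendix 1 define the routine safety laboratory as hematology, chemistry and urinalysis, both on treatment and in the safety follow-up (SFU).

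The synopsis and Section 2 make "Change from baseline in clinical laboratory test results" a secondary safety endpoint. Section 6.6 summarises it by time, together with clinically significant abnormalities.

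**The concern.** The protocol reports kidney findings in animals and then schedules a broad chemistry panel, with amylase, lipase, uric acid, CPK and triglycerides, that has no serum marker of filtration. It gives no reason for leaving one out.

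What is at stake is what the report can say. If the plan is followed as written, the laboratory safety endpoint will hold no scheduled filtration result. A fall in filtration without a dipstick change would not be recorded by any scheduled test. Section 1.3 calls this the first trial of ocrelizumab in pediatric patients, so laboratory data on this point from children cannot be taken from an earlier study of the drug.

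**Working it through.** **1. Length of observation (the plan's own figure first).** Section 3.3 gives about 402 weeks per patient, from screening to the end of the SFU.
- Inputs: maximum screening 10 weeks (Section 3.1.1.1), treatment 24 + 264 = 288 weeks, SFU 104 weeks (Section 3.1.1.4).
- 10 + 288 + 104 = 402 weeks, and 402 / 52.18 = 7.7 years. The figure is reproduced.
- From first dose, with SFU visits counted from Week 288: 288 + 104 = 392 weeks = 7.5 years.
- From first dose, with the SFU counted from the last scheduled infusion at Week 264: 264 + 104 = 368 weeks = 7.1 years.
- Prolonged B-cell monitoring would add to either figure.

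**2. The panel, item by item.**
- First part: AST, ALT, gamma glutamyl transferase, alkaline phosphatase, amylase, lipase, total protein, albumin, cholesterol, total bilirubin = 10.
- Second part: uric acid, potassium, sodium, chloride, calcium, phosphorus, LDH, CPK, triglycerides = 9.
- Total 10 + 9 = 19, not counting reflex bilirubin fractions. Creatinine, urea (BUN) and cystatin C: 0 of 19.
- The list is worded as complete. By contrast, the biomarker list in Section 4.5.19.7 is expressly open-ended.

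**3. Other places where a filtration marker could have been added.** None has one:
- screening tests (Section 4.5.19.3)
- laboratory exclusions (Section 4.1.2.3)
- re-treatment criteria (Section 4.3.6)
- the schedules in Appendix 1 (Tables 1, 2a, 2b and 3)

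**4. The animal findings.** Glomerulopathy 7/24 = 29.2%; kidney inflammation 2/24 = 8.3%. The counts are given for the two dose levels together, with no split by dose and no control rate beside them. They are observed proportions, not excess risks.

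**5. What the scheduled tests do cover.** The dipstick screens for blood and protein, with microscopy on an abnormal result. The panel has albumin, total protein, potassium, phosphorus, calcium and uric acid. None of these gives an estimate of filtration.

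**6. Samples already available.** Chemistry is drawn at screening, Day 1 and Weeks 2, 12 and 22 (5 visits; Week 24 only if missed at Week 22). It is then drawn repeatedly in the extension, and at SFU Weeks 12, 24, 36, 48, 60, 72, 84, 96 and 104 (9 visits). Height, needed for a pediatric filtration estimate, is measured about every 6 months (Section 4.5.6) and yearly in prolonged B-cell monitoring.

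**The case against.** The strongest reply is that kidney surveillance is neither absent nor trivial. A dipstick for blood and protein with reflex microscopy looks for the kind of injury seen in the monkeys. It recurs throughout treatment and at all nine SFU visits. Section 4.5.19 also allows unscheduled safety tests at any time, so an investigator who suspects a problem can order creatinine. All of this stands. A reader might infer that renal function cannot be measured in this trial; the documents do not support that.

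The second reply concerns the signal. It came from a pre- and post-natal study at about 5 and 25 times the clinical dose. General toxicology studies at up to 100 mg/kg showed no adverse findings, and the account of the juvenile study mentions no kidney finding. Sections 5.1.1 and 5.1.2 list no renal toxicity, and the adult summary in Section 1.2.4.2, covering 825 and 486 ocrelizumab patients, describes none. This also stands, and it lowers the expected risk. It is not stated anywhere as a reason for leaving out a filtration marker. The 5-fold and 13-fold exposure margins come from the juvenile study, so they are not margins for the kidney findings.

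Third, the laboratory endpoint names no renal parameter, so it is not unmet. That is correct; the endpoint is only less informative than it could be. Fourth, the Laboratory Manual is not among the documents and may list more analytes. If it does, the protocol should say so.

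**Conclusion.** The concern holds in a limited form. No scheduled test gives a serum marker of filtration over about 7.1 to 7.5 years after first dose, and scheduled kidney surveillance rests on a semi-quantitative dipstick with reflex microscopy. This is an inexpensive improvement that should be made, not a flaw that undermines the trial.

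Three stronger readings go beyond the documents:
- **Expected renal harm in children at the study doses.** The animal doses were higher, the findings are attributed only tentatively to immunosuppression, and no human renal signal is described.
- **A stated chance of missing a case.** The documents give no rate of creatinine change, so any such probability would rest on an invented input.
- **A special gap around gadolinium contrast at baseline and Week 12.** No section links contrast to a renal value.

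The conclusion assumes that the list in Section 4.5.19.2 is what the central laboratory runs.

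**What to change.** Add serum creatinine and urea to the chemistry list in Section 4.5.19.2, run on the samples already drawn at routine safety laboratory visits. Patients already enrolled start at their next scheduled sample.

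In Section 6.6:
- Report change from baseline only for patients with a pre-dose value. Cohort 2 is closed to enrolment, so this means at most patients still to enter Cohort 1.
- For all others, summarise values over time and abnormalities against age-appropriate reference ranges. Section 6.6.2.1 applies the Sponsor's standard ranges and does not say whether they are age-specific.
- Say how the rule in Section 6.6.2.2 applies, since it replaces a missing baseline with the midpoint of the reference range when marking abnormalities. It should not create a change from baseline.
- Report estimated filtration at visits where height is measured, with a stated pairing window. In Table 1 and the early part of Table 2a, the required sample falls two weeks before the height visit (Weeks 22 and 24, 46 and 48, 70 and 72).

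If the Sponsor prefers not to add the analytes, the protocol should state why dipstick surveillance is enough given Section 1.2.1.

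The cost is a small assay charge and a line each in the protocol and Laboratory Manual, with no extra visit. The limit that cannot be removed is that children already enrolled have no pre-treatment value.
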